1 PROTOCOL SUMMARY

1.1 SYNOPSIS

Title: A randomized, placebo-controlled, double-blinded cross-over study of the pharmacologic action of a GPR119 agonist on glucagon counter-regulation during insulin-induced hypoglycemia in Type 1 diabetes mellitus.

Study Description: This is a placebo-controlled, double-blinded, within-subject, cross-over Phase 2a study to test the hypothesis that short term (14-day) administration of MBX-2982, a G-protein coupled receptor-119 (GPR119) small molecule agonist, will significantly increase the glucagon counter-regulatory response to hypoglycemia in individuals with Type 1 Diabetes Mellitus (T1DM).

Objectives: Primary objective:

- To compare (relative to placebo treatment) the effect of MBX-2982, a GPR119 agonist, on glucagon counter-regulatory responses to insulin-induced hypoglycemia in subjects with T1DM.

Secondary objectives:

- To determine whether MBX-2982, through its effect upon glucagon counter-regulation, increases hepatic glucose production (HGP) during insulin-induced hypoglycemia and during recovery to euglycemia in subjects with T1D relative to placebo treatment.
- To determine whether MBX-2982 reduces time of recovery from hypoglycemia to euglycemia in T1DM relative to placebo treatment.
- To determine whether there is any effect of MBX-2982 upon other key counter-regulatory hormones in T1D relative to placebo treatment.
- To compare the glucagon counter-regulatory response in healthy (non-diabetic) volunteers during insulin-induced hypoglycemia to that of subjects with T1DM treated with MBX-2982 and placebo.
- To compare time to recovery to euglycemia from insulin-induced hypoglycemia in healthy (non-diabetic) volunteers to that of subjects with T1DM treated with MBX-2982 and placebo.
- To compare the hepatic glucose production response to insulin-induced hypoglycemia in healthy (non-diabetic) volunteers to that of subjects with T1DM treated with MBX-2982 and placebo.

Exploratory objectives:

- To evaluate the effects of MBX-2982 upon fasting and postprandial glucagon, GLP-1 and GIP concentrations in subjects with T1DM relative to placebo treatment.
- To evaluate the effects of MBX-2982 on patterns of glycemia determined by continuous glucose monitoring in subjects with T1DM relative to placebo.
- To evaluate the pharmacokinetic profile of MBX-2982 in subjects with T1DM.

Endpoints:**Primary Endpoint:**

- The glucagon response to hypoglycemia defined as:

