 - Maximal glucagon concentration during hypoglycemia
 - Total area under the curve (AUC) for glucagon during hypoglycemia.
 - Incremental AUC for glucagon during hypoglycemia (above baseline levels during euglycemia).

Measured in subjects with T1D treated with MBX-2982 relative to placebo.

Secondary and Exploratory Endpoints:

- The glucagon response to hypoglycemia defined as:
 - Maximal glucagon concentration during hypoglycemia
 - Total area under the curve (AUC) for glucagon during hypoglycemia.
 - Incremental AUC for glucagon during hypoglycemia (above baseline levels during euglycemia).

Measured in subjects with T1D treated with MBX-2982 or placebo relative to healthy controls.

- HGP during insulin-induced hypoglycemia
- HGP during recovery from insulin-induced hypoglycemia to euglycemia
- Time of recovery from hypoglycemia (time to reach 85 mg/dL)
- Plasma levels of counter regulatory hormones during hypoglycemia including epinephrine, cortisol, GH.
- Fasting and post-prandial levels of glucagon, GLP-1 and GIP.

All measured in subjects with T1D treated with MBX-2982 relative to placebo and relative to healthy controls.

- Continuous glucose monitoring (CGM) indices of glycemic control including hypoglycemia (percent of time < 70 mg/dL, < 54 mg/dL), hypoglycemic events, mean glucose, percent of time 70-180 mg/dL, percent of time > 180 mg/dL, percent of time > 250 mg/dL, glycemic variability.
- MBX-2982 plasma levels

Measured in subjects with T1D treated with MBX-2982 relative to placebo.

Study Population:

The study will recruit 20 participants with T1DM fulfilling the following criteria:

- Age 20-60 years
- Diagnosis of T1DM according to American Diabetes Association (ADA) criteria continuously requiring insulin for survival
- Diabetes diagnosis performed more than 5 years before enrollment
- Fasting C-peptide levels < 0.7 ng/mL with a concurrent plasma glucose concentration > 90 mg/dL (Labs may need to be repeated if FBG \leq 90)

- For female participants: agrees not to become pregnant during the study and for at least 2 weeks after the last dose of the study medication.
- For male participants: agrees not to donate sperm and to avoid getting a woman pregnant during the study and for at least 2 weeks after the last dose of the study medication.

A cohort of 9 healthy volunteers will also be recruited, fulfilling the following criteria:

[figure not shown]
- Age 20 -60 years
- General good health

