3 OBJECTIVES AND ENDPOINTS

Primary Objectives and Endpoints	
Objective	Endpoint
To compare (relative to placebo treatment) the effect of MBX-2982, a GPR119 agonist, on glucagon counter-regulatory responses to insulin-induced hypoglycemia in subjects with T1DM.	Maximal glucagon concentration during hypoglycemia. Total area under the curve (AUC) for glucagon during hypoglycemia. Incremental AUC for glucagon during hypoglycemia (above baseline levels during euglycemia)
Secondary Objectives and Endpoints	
Objectives	Endpoint
To determine whether MBX-2982, through its effect upon glucagon counter-regulation, increases hepatic glucose production (HGP) during insulin-induced hypoglycemia and during recovery to euglycemia in subjects with T1D relative to placebo treatment.	HGP during insulin-induced hypoglycemia. HGP during recovery from insulin-induced hypoglycemia to euglycemia.
To determine whether MBX-2982 reduces time of recovery from hypoglycemia to euglycemia in T1DM relative to placebo treatment	Time of recovery from hypoglycemia (time to reach 85 mg/dL).
To determine whether there is any effect of MBX-2982 upon other key counter-regulatory hormones in T1D relative to placebo treatment	Plasma levels of counter regulatory hormones during hypoglycemia including epinephrine, cortisol, GH.
To compare the glucagon counter-regulatory response in healthy (non-diabetic) volunteers during insulin-induced hypoglycemia to that of subjects with T1DM treated with MBX-2982 and placebo.	Total area under the curve (AUC) for glucagon during hypoglycemia Incremental AUC for glucagon during hypoglycemia (above baseline levels during euglycemia) Plasma levels of counter regulatory hormones during hypoglycemia including epinephrine, cortisol, GH.
To compare time to recovery to euglycemia from insulin-induced hypoglycemia in healthy (non-diabetic) volunteers to that of subjects with T1DM treated with MBX-2982 and placebo	Time of recovery from hypoglycemia.
To compare the hepatic glucose production response to insulin-induced hypoglycemia in healthy (non-diabetic) volunteers to that of subjects with T1DM treated with MBX-2982 and placebo	HGP during insulin-induced hypoglycemia. HGP during recovery from insulin-induced hypoglycemia to euglycemia.

Exploratory Objectives and Endpoints	
Objective	Endpoint

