10 STATISTICAL CONSIDERATIONS

10.1 STATISTICAL HYPOTHESES

For the primary endpoints, we hypothesize that the medication (14-day administration of MBX-2982) will increase the measured glucose counter-regulation to hypoglycemia expressed as the maximal glucagon concentration, AUC, and Incremental AUC (iAUC) for glucagon during hypoglycemia compared to placebo. For the secondary endpoints, we hypothesize that the medication:

- will increase hepatic glucose production during insulin-induced hypoglycemia and during a subsequent recovery to euglycemia;
- will reduce the time of recovery from hypoglycemia to euglycemia;
- will increase other counter-regulatory hormones;
- the above-mentioned effects will approach the counter-regulatory response in healthy (non-diabetic) volunteers during insulin-induced hypoglycemia;

Exploratory analysis will:

- evaluate for any effects of a GPR119 agonist upon fasting and/or postprandial glucagon concentrations in T1DM, together with potential effects on fasting and postprandial, GLP-1 and GIP;
- collect data patterns of glycemia of participants with T1DM while are receiving daily therapy with a GPR119 agonist (or placebo);
- evaluate the pharmacokinetic profile of MBX-2982 in participants with T1DM.

10.1.1.1 PRIMARY EFFICACY ENDPOINT(S):

- Maximal glucagon concentration during hypoglycemia
- Total area under the curve (AUC) for glucagon during hypoglycemia
- Incremental AUC for glucagon during hypoglycemia above baseline levels during euglycemia

10.1.1.2 SECONDARY EFFICACY ENDPOINT(S):

- HGP during insulin-induced hypoglycemia
- HGP during recovery from insulin-induced hypoglycemia to euglycemia
- Time of recovery from hypoglycemia (time to reach 85 mg/dL)
- Plasma levels of counter regulatory hormones during hypoglycemia: epinephrine, cortisol, GH

10.1.1.3 EXPLORATORY ENDPOINT(S):

- Levels of GLP-1, GIP in fasting and post-prandial conditions
- Continuous glucose monitoring (CGM) indices of glycemic control including hypoglycemia (percent of time < 70 mg/dL, < 54 mg/dL), hypoglycemic events, mean glucose, percent of time 70-180 mg/dL, percent of time > 180 mg/dL, percent of time > 250 mg/dL, glycemic variability.
- MBX-2982 plasma levels

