10.2 SAMPLE SIZE DETERMINATION

It is not precisely known how much of an improvement in glucagon counter-regulation is needed to be clinically significant for mitigating risk of hypoglycemia. Restoring glucagon counter-regulation to levels observed in people without diabetes would meet and quite likely exceed expectations, this may be too high a bar by which to judge success or failure in this initial short-term study. We estimate that a lower boundary of meaningful therapeutic effect would be at least a 30% increase in glucagon counter-regulation and have used this criterion to estimate sample size for the current study.

According to a published study that measured glucagon counter-regulation to hypoglycemia in T1DM (19), of the 28 T1DM subjects, the maximal glucagon concentration in placebo treated T1DM group during hypoglycemia was 23 pmol/l, while the standard deviation was 10.4 pmol/l. To apply these statistics in the current crossover design, 16 subjects are required to detect a 30% increase (6.9 pmol/l) in the GPR119 agonist treated group compared to a placebo treated group, this will have an 0.8 power, assuming a 0.5 correlation coefficient between two treatments within the same subjects, and a one-sided paired t-test at 0.05 significant level. Accounting for a potential (up-to) 25% dropout rate, 20 T1DM subjects are expected to be recruited to the current study. A sample size of 9 Healthy subjects should be adequate to establish the normative (descriptive) data using the same assays and clamp procedures as being used for T1DM.

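### Three unranked primary glucagon measures have no success rule, and the stated 0.05 alpha and 0.8 power belong to the maximal-glucagon test alone

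*Combined protocol and SAP*

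**What the plan says.** The Synopsis (Section 1.1) has a single primary endpoint, introduced as "The glucagon response to hypoglycemia defined as" and followed by three measures: maximal concentration, total AUC, and incremental AUC over the euglycemic baseline. Section 3 lists the same three against the primary objective, beginning "Maximal glucagon concentration during hypoglycemia. Total area under the curve (AUC) for glucagon during hypoglycemia". Section 10.1 uses the plural, "For the primary endpoints, we hypothesize that the medication", and gives the hypothesis as an increase "expressed as the maximal glucagon concentration, AUC, and Incremental AUC (iAUC) for glucagon during hypoglycemia compared to placebo".

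Section 10.2 sizes the trial on one of the three. Its source figure is that "the maximal glucagon concentration in placebo treated T1DM group during hypoglycemia was 23 pmol/l", with SD 10.4 pmol/l and a target increase of 30% (6.9 pmol/l). The test is "a one-sided paired t-test at 0.05 significant level", with a within-subject correlation of 0.5, power 0.8 and 16 subjects required. On attrition: "Accounting for a potential (up-to) 25% dropout rate, 20 T1DM subjects are expected to be recruited to the current study". No mean, SD or effect is given for either AUC.

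Section 10 runs from hypotheses through sample size, randomization and blinding to oversight and data handling. Neither the text nor the table of contents shows a statistical analysis section that could hold a decision rule.

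**The concern.** With three primary measures and no rule, the plan does not define what meeting the primary hypothesis means. One endpoint described three ways, three co-primaries that must all succeed, and three alternatives of which any may succeed have different type I error and power. The wording, singular in Section 1.1 and plural in Section 10.1, does not settle the choice. The one alpha and one power figure in the plan describe one test and not the three-measure hypothesis.

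Section 2.1 presents the study as a step toward larger and longer trials, and Section 10.2 speaks of judging success or failure. If the measures disagree, the rule could be chosen after the results are seen. The measures can differ for a substantive reason. Incremental AUC subtracts the euglycemic baseline and the other two do not, and Section 4.2 takes seriously that the drug might raise fasting glucagon.

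**Working it through.** **Step 1: reproduce the plan's figure.** Inputs from Section 10.2: effect 0.30 × 23 = 6.9; SD 10.4; within-subject correlation 0.5; one-sided alpha 0.05.

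- SD of the paired difference = 10.4 × √(2 × (1 − 0.5)) = 10.4.
- Standardised effect = 6.9 / 10.4 = 0.663.
- Exact power comes from the noncentral t with n − 1 degrees of freedom and noncentrality 0.663 × √n.

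Power is 0.787 at n = 15, 0.812 at n = 16 and 0.888 at n = 20. The smallest n reaching 0.8 is 16, as stated. The sizing is correct for maximal glucagon.

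**Step 2: the attrition figure.** 20 × (1 − 0.25) = 15 completers, one short of 16, so the full stated dropout leaves power 0.79 for that test. (20 equals 16 × 1.25, whereas 16 / 0.75 rounds up to 22.)

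**Step 3: what each possible rule would imply.** The documents give no correlation between the three measures and no AUC effects, so everything from here is an illustration. Three equally correlated paired differences were simulated at n = 16, each tested at one-sided 0.05 (200,000 trials per cell). The power and equal-effects columns give both AUCs the standardised effect of maximal glucagon, 0.663. Split means that at least one measure is significant and at least one is not.

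| Assumed correlation | Any-of-three: type I error | All-three: power | Two-of-three: error (all null) / power | Split, all null | Split, equal effects |
|---|---|---|---|---|---|
| 0.5 | 0.121 | 0.625 | 0.026 / 0.853 | 0.118 | 0.332 |
| 0.7 | 0.104 | 0.671 | 0.034 / 0.835 | 0.092 | 0.259 |
| 0.9 | 0.080 | 0.734 | 0.044 / 0.820 | 0.054 | 0.149 |
| 0.95 | 0.072 | 0.757 | 0.047 / 0.816 | 0.041 | 0.107 |

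The null split column follows from the others. Each test rejects with probability 0.05, so 3 × 0.05 = 0.15 = P(at least one) + P(at least two) + P(all three). At correlation 0.9, P(all three) = 0.15 − 0.080 − 0.044 = 0.026, and the split rate is 0.080 − 0.026 = 0.054.

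**Step 4: sensitivity to n and to the AUC effects.** With 15 completers and equal effects, all-three power at correlation 0.9 to 0.95 is 0.70 to 0.73, and 12% to 16% of trials split. If the AUC standardised effects are 0.5 instead (assumption), all-three power at n = 16 is 0.53 to 0.55 and 26% to 29% split. If they are 0.8, all-three power is 0.80 to 0.81.

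**The case against.** The strongest reply has four parts.

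First, this is a proof-of-pharmacology study making no confirmatory claim, and Section 2.1 says pivotal trials would follow. Formal multiplicity control over three summaries of one hormone curve may be more than it needs. That limits the weight of the point. It does not supply the missing criterion, and naming a lead measure is a modest request.

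Second, Section 10.1 joins the measures with a conjunction. A reader might infer that all three must succeed, in which case type I error cannot exceed 0.05. Nothing says that each must be significant, so this rests on grammar alone. The opposite inference, that the plan adopts any-of-three and therefore runs at an inflated error rate, has no better support. Each is one possible reading.

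Third, sizing on one endpoint is routine, and Section 10.2 is open about it. That stands. A reader might infer that the sample size is wrong, but 16 reproduces for the test it describes.

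Fourth, the multi-measure figures rest on assumed correlations. That also stands: 0.9 to 0.95 is neither documented nor a bound, and equal correlation is doubtful because only incremental AUC removes the baseline. With an illustrative correlation of 0.95 between peak and total AUC, and 0.6 of each with incremental AUC, any-of-three error is 0.10, all-three power 0.69 and the split rate 24% at n = 16. The 11% to 15% split rate also presumes a real effect on all three. Under the null, where a favourable choice of rule would produce a false claim, it is about 4% to 6% at the same correlations.

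**Conclusion.** The gap is real and should be fixed. Three primary measures are named with no ranking, success rule or multiplicity control, and the stated alpha and power apply to maximal glucagon only. Under any-of-three, type I error is about 0.07 to 0.12 (assumed correlation 0.95 to 0.5). Under all-three, power with 16 completers is about 0.76 to 0.63 (same correlations, equal effects assumed). At correlation 0.9 to 0.95 the measures would disagree in about 4% to 6% of null trials and 11% to 15% of trials with equal true effects, and more often if correlations are lower.

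A reader might go further and infer that 0.05 and 0.8 cannot both hold with three measures. The documents do not support that. Under the equal-effects assumption, a two-of-three rule gives error 0.044 to 0.047 when all three are null and power 0.82 at correlation 0.9 to 0.95. The defect is the unstated rule.

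Confidence is high on the omission and on the single-test power. The remaining figures are only as good as the assumed correlations and AUC effects.

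**What to change.** Provided the treatment code has not been broken, make these wording changes:

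- In Sections 1.1, 3 and 10.1, name maximal glucagon during hypoglycemia as the single primary endpoint at one-sided 0.05. It leads because it is the only measure with a power calculation.
- Test the two AUCs only after it succeeds, in fixed sequence, each at one-sided 0.05 and only after success on the one before. The documents give no basis for ranking one AUC over the other, so the sponsor should choose the order and state it in advance.
- In Section 10.2, state that power applies to maximal glucagon only: 0.81 with 16 completers and 0.79 with the 15 left after 25% dropout from 20.

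A stated all-three or two-of-three rule would also close the gap. All-three lowers power under equal effects. Two-of-three is met in about 7% of trials when only maximal glucagon has an effect (n = 16, correlation 0.9 to 0.95).

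No new patients or data are needed. The timing condition matters. Section 4.6 rules out interim analysis and Section 10.4 makes the pharmacist the only unblinded person, but the amendment history (Section 11, V8.0) records 10 completed participants with type 1 diabetes, and the documents do not show current status. The sponsor should confirm that the code is intact and date the change.

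The price is that the AUCs cannot carry the primary claim alone. At n = 16 and correlation 0.9 to 0.95, power along the sequence is 0.81, then 0.76 to 0.78, then 0.73 to 0.76 with equal effects. With AUC standardised effects of 0.5 (assumption), the second and third steps fall to about 0.60 and 0.53 to 0.55.

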10.2 SAMPLE SIZE DETERMINATION

It is not precisely known how much of an improvement in glucagon counter-regulation is needed to be clinically significant for mitigating risk of hypoglycemia. Restoring glucagon counter-regulation to levels observed in people without diabetes would meet and quite likely exceed expectations, this may be too high a bar by which to judge success or failure in this initial short-term study. We estimate that a lower boundary of meaningful therapeutic effect would be at least a 30% increase in glucagon counter-regulation and have used this criterion to estimate sample size for the current study.

According to a published study that measured glucagon counter-regulation to hypoglycemia in T1DM (19), of the 28 T1DM subjects, the maximal glucagon concentration in placebo treated T1DM group during hypoglycemia was 23 pmol/l, while the standard deviation was 10.4 pmol/l. To apply these statistics in the current crossover design, 16 subjects are required to detect a 30% increase (6.9 pmol/l) in the GPR119 agonist treated group compared to a placebo treated group, this will have an 0.8 power, assuming a 0.5 correlation coefficient between two treatments within the same subjects, and a one-sided paired t-test at 0.05 significant level. Accounting for a potential (up-to) 25% dropout rate, 20 T1DM subjects are expected to be recruited to the current study. A sample size of 9 Healthy subjects should be adequate to establish the normative (descriptive) data using the same assays and clamp procedures as being used for T1DM.

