7.2.3 DATA COLLECTION AND FOLLOW-UP FOR WITHDRAWN SUBJECTS

Participants who request withdrawal or who are withdrawn by the PI from the study will have their data maintained in the research database up to the point of withdrawal. The available data will be included in subsequent analysis because a participant may have withdrawn due to possible drug side effects (if applicable) and keeping these participants in the analysis is essential for study validity.

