10.3 RANDOMIZATION

Randomization schedule based on the two-treatment, two-period, two-sequence cross-over design for 20 patients will be generated by a biostatistician using SAS (9.4). The treatment assignments will be coded as A or B. This information will only be released as the patients are enrolled. The message communicating group assignment will be saved in the subject's study file.

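### Section 10.2 overstates the dropout allowance: 20 T1DM subjects keep the required 16 completers up to 20% dropout, not 25%; the effect on power is small

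*Combined protocol and SAP*

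**What the plan says.** Section 10.2 sizes the T1DM cohort on maximal glucagon during hypoglycemia. It takes its inputs from a published study: "the maximal glucagon concentration in placebo treated T1DM group during hypoglycemia was 23 pmol/l", and "the standard deviation was 10.4 pmol/l". The target is to "detect a 30% increase (6.9 pmol/l) in the GPR119 agonist treated group compared to a placebo treated group", with 0.8 power and a one-sided paired t-test at 0.05, "assuming a 0.5 correlation coefficient between two treatments within the same subjects". This gives 16 subjects. The dropout step follows: "Accounting for a potential (up-to) 25% dropout rate, 20 T1DM subjects are expected to be recruited to the current study".

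Section 10.3 plans the randomization schedule for the same number, a "two-treatment, two-period, two-sequence cross-over design for 20 patients". The synopsis, Section 4.5 and Section 7.1 also use 20 T1DM subjects. Section 7.2.3 says of withdrawn subjects: "The available data will be included in subsequent analysis because a participant may have withdrawn". No section describes replacing a subject who drops out.

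**The concern.** A dropout rate is a fraction of the subjects who enter. If a quarter of 20 are lost, 15 remain, one fewer than the number that the preceding sentence calls required. The 25% in the text is the ratio of extra recruits to completers (4/16), which is a different quantity.

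What is at stake is the assurance given to the IRB and to later readers that the design still has its required number at the worst dropout rate it plans for. As written, it does not. The open questions are how far power falls, and whether another part of the plan makes up the difference.

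**Working it through.** **Inputs (all from Section 10.2).** Placebo mean 23 pmol/l; difference δ = 0.30 × 23 = 6.9 pmol/l; SD 10.4 pmol/l; within-subject correlation ρ = 0.5; one-sided α = 0.05; paired t-test; target power 0.8; dropout up to 25%; 20 recruited.

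**Step 1: reproduce the 16.** The SD of the within-subject difference is

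SD_d = 10.4 × √(2 × (1 − 0.5)) = 10.4 pmol/l,

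so the standardized difference is 6.9 / 10.4 = 0.663. Power is P(T > t₀.₉₅,ₙ₋₁), where T has a noncentral t distribution with n − 1 degrees of freedom and noncentrality 0.663 × √n.

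| Completers | Losses out of 20 | Dropout | Power |
|---|---|---|---|
| 20 | 0 | 0% | 0.888 |
| 19 | 1 | 5% | 0.872 |
| 18 | 2 | 10% | 0.854 |
| 17 | 3 | 15% | 0.835 |
| 16 | 4 | 20% | 0.812 |
| 15 | 5 | 25% | 0.787 |

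Sixteen is the smallest n with at least 0.80 power, so the plan's base figure reproduces. Taking one degree of freedom for a period effect (n − 2) changes little: 0.810 at n = 16 and 0.784 at n = 15.

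**Step 2: check the 20.**

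- Inflating by the rate: 16 × (1 + 0.25) = 20. This matches the plan.
- Allowing for a dropout rate: 16 / (1 − 0.25) = 21.33, rounded up to 22.
- Rate that 20 recruits can absorb: 1 − 16/20 = 20%.
- Completers at the stated ceiling: 20 × 0.75 = 15.

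**Step 3: size of the shortfall at 25%.** Power is 0.787, which is 0.013 below 0.80 and 0.025 below the 0.812 at n = 16. Equivalently, the difference detectable with 80% power is 7.02 pmol/l with 15 completers (7.02 / 23 = 30.5%), against 6.78 pmol/l with 16 (29.5%).

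**Step 4: could data from withdrawn subjects make up the loss?** A subject with only one clamp adds nothing to the paired t-test on which the 16 rests. Section 7.2.3 keeps such data, but the documents name no model that would use them. As an illustration, assume a mixed model with a period effect and ρ = 0.5.

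- All 5 dropouts leave after the first clamp, evenly split by sequence: each adds about a quarter of a pair, so 15 + 5 × 0.25 = 16.25 effective pairs, with power about 0.81 (13 to 14 degrees of freedom).
- All 5 leave before the first clamp, or all come from one sequence: effective pairs stay at about 15, with power about 0.79.

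Power at the 25% ceiling therefore lies between about 0.79 and 0.81, depending on who leaves, when, and which analysis is used.

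**The case against.** The strongest case against the point is that it is close to immaterial.

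- The plan states power to one decimal, and 0.787 rounds to 0.8.
- The shortfall is smaller than the uncertainty in the assumed correlation. With 15 completers and ρ = 0.52, power is 0.802; with 16 completers and ρ = 0.48, it is 0.799. A shift of 0.02 in an assumed input does as much as the error.
- The 25% is a ceiling, not an expected rate. Section 7.1 also stops the study if a discontinuation event occurs in more than 15% (n = 3) of the planned 20. If that rule pools all the listed events, five losses in a study that runs to the end would have to include at least two for other reasons. The rule could also be read per event type, so it limits this scenario without excluding it.
- The numbers are not rigid. Section 10.2 speaks of expected recruitment, Section 4.5 calls its numbers estimates, and no text forbids extending the schedule.

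All of this bears on size and stands as such: the point is no ground for calling the trial underpowered or for enlarging it. None of it makes 25% the right figure. A flexible recruitment number is also not a replacement rule, and no section restates the allowance correctly.

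**Conclusion.** The concern holds and is minor. The base size of 16 is right; the dropout allowance attached to 20 recruits is wrong. Twenty T1DM subjects preserve 16 completers up to 20% dropout. At the stated 25% they leave 15, with power 0.787 in place of at least 0.80. With four or fewer losses the target is met.

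The 20% and the 15 completers are plain arithmetic on Section 10.2's own numbers. The power figures rest on that section's difference, SD, correlation and one-sided paired t-test. Whether data from subjects with a single clamp would recover the loss cannot be settled, because the documents name the paired t-test only for sizing and specify no model for incomplete pairs.

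**What to change.** Keep 20 subjects and replace the dropout sentence in Section 10.2 with, for example:

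> *With 20 T1DM subjects recruited, up to 20% dropout leaves 16 completers (power 0.81); at 25% dropout, 15 complete (power about 0.79).*

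The cost is one sentence. It adds no patients and changes no test, endpoint, randomization schedule or study conduct; the stated allowance simply becomes slightly less favorable. Keeping the 25% allowance would instead need 22 recruits, which a gap of 1.3 percentage points at the ceiling does not call for.
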